2.6.4 REPORT

The Immune Report Card report is generated as a PDF and provides relevant patient and sample information, immune marker results, therapeutic associations and key references. Additionally, each report has a summary interpretation provided by a board-certified pathologist. The report is generated in approximately 5 days of receipt of tissue by OmniSeq.

3.0 STUDY OBJECTIVES

3.1 PRIMARY OBJECTIVE

Estimate the probability of objective response to treatment determined by gene expression of LAG3 and CTLA4 per Omniseq Immune Report card in R/M HNSCC patients who have progressed on prior immunotherapy.

3.2 SECONDARY OBJECTIVES

1. Estimate the disease control rate (DCR), progression-free survival (PFS), overall survival (OS) and safety of treatment determined by gene expression of LAG3 and CTLA4 per Omniseq Immune Report card for R/M HNSCC patients who have progressed on prior immunotherapy;
2. Estimate the probability of objective response, DCR, PFS, OS and safety of treatment that is randomly assigned instead of determined by gene expression. This will be compared in an exploratory fashion to the objective response of those patients with treatment determined by gene expression.
3. Estimate the probability of objective response, Disease control rate (DCR)PFS, OS and safety of treatment determined by gene expression of LAG3 and CTLA4 per Omniseq Immune Report card for R/M HNSCC patients who have progressed on trial treatment and undergo a second biopsy and second treatment determined by a second gene expression analysis of LAG3 and CTLA4.;

3.3 Exploratory Biomarker studies:

- A. Evaluate immune gene expression, immune co-signaling molecule expression by IHC, and immune cell populations over time via paired samples after exposure to combination immunotherapy;
- B. Evaluate co-signaling molecule expression by IHC and correlate with gene expression by RNAseq as well as the predictive value of co-signaling molecule expression by IHC and the efficacy of the combination selected;
- C. Evaluate immune cell populations and other biomarkers (as per section 14.0) in the peripheral blood at baseline and over time;
- D. Evaluate saliva and stool microbiome to determine if any correlation with efficacy of the combination selected.

4.0 INVESTIGATIONAL PLAN

4.1 SUMMARY

Each patient's tumor biopsy sample will be analyzed for gene expression for CTLA4 and LAG3 using the OmniSeq Immune Report Card. The drug to be added to Nivolumab will be based on which relevant gene has the highest relative rank expression score (CTLA4 or LAG3) assuming that the difference between the relative rank score of the two genes are atleast 15.2 (as per the treatment assignment rule (section 15.0). For example, if analysis shows that LAG-3 is at least 15.2 higher than CTLA-4 then the patient will receive Nivolumab plus Relatlimab. If the difference between CTLA4 and LAG3 is less than 15.2 than the patient will be randomly assigned 1:1 to either Ipilimumab plus Nivolumab or Relatlimab plus Nivolumab. Because the relative efficacy of the two combinations has not been established in anti-PD-1/PD-L1 failure HNSCC patients, there is equipoise for randomizing if the minimum difference in relative rank score is not met. The patient will then receive the

prescribed therapy continuously for up to 24 cycles (1 cycle = 4 weeks of treatment), with repeat imaging prior to every 3rd cycle. RECIST 1.1 with modifications, to allow for continued therapy until progressive disease is confirmed if the patient is clinically stable, will be used in the trial. If the patient has confirmed progression and meets eligibility criteria to obtain a second biopsy (section 7.4), the patient will continue on trial and undergo a repeat biopsy for gene expression of LAG3 and CTLA4 per OmniSeq Immune Report Card to select another agent to add to Nivolumab (see section 7.6 below). The patient will then be treated with this new combination continuously, with repeat imaging prior to every 3rd cycle as per initial treatment, until progression of disease (see Schema A).

5.0 INCLUSION/EXCLUSION CRITERIA

5.1 INCLUSION CRITERIA

1. Recurrent and/or Metastatic squamous cell carcinoma of the head and neck that is not amenable to therapy with curative intent. Patients who refuse salvage surgery or radiation for recurrence are eligible.
2. Failure of prior immunotherapy as defined as:
 - a. Progression of disease on anti-PD-1 mAb or anti-PD-L1 mAb treatment in the R/M setting.
 - b. Both patients that have received platinum based chemotherapy prior or have not yet received platinum based chemotherapy are eligible.
3. Patients cannot have received more than 3 total lines of prior systemic therapy in the recurrent/metastatic setting
4. ECOG performance status of 0-1
5. Have at least one measurable area of disease (Target Lesion) based on RECIST 1.1.
6. Provide adequate tissue (core or incisional/excisional biopsy) prior to starting study for analysis for gene expression of LAG3 and CTLA4 per OmniSeq Immune Report Card. FNA is not adequate. Archival tissue can only be used if it was obtained in the recurrent/metastatic setting and there has been no subsequent cancer treatment after that tissue was obtained.
7. Life expectancy of at least 12 weeks based on investigator estimate.
8. Age \geq 18 years old
9. LVEF assessment with documented LVEF \geq 50% by either TTE or MUGA (TTE preferred test) within 6 months from first study drug administration
10. Patients must have normal organ and marrow function as defined below:

– absolute neutrophil count	\geq 1,500/mcL
– platelets	\geq 100,000/mcL
– total bilirubin	\leq institutional upper limit of normal (ULN)
– AST(SGOT)/ALT(SGPT)	\leq 2.5 \times institutional ULN
– creatinine	\leq institutional ULN

OR

– glomerular filtration rate \geq 40 mL/min/1.73 m ² for patients with creatinine levels (GFR) above institutional normal.	
---	--
10. Female subjects of childbearing potential must have a negative urine or serum pregnancy test within 28 days prior to receiving the first dose of study medication. If the urine test is positive or cannot be confirmed as negative, a serum pregnancy test will be required. Pregnancy testing will be repeated on C1D1 prior to the first doses of study medication.

11. Female subjects of childbearing potential should be willing to use 1 method of birth control or abstain from heterosexual activity for the course of the study through 24 weeks after the last dose of study medication. Women of childbearing potential are those who have not been surgically sterilized or have not been free from menses for > 1 year.
12. Male subjects should agree to use an adequate method of contraception starting with the first dose of study therapy through 7 months after the last dose of study therapy.
13. Ability to understand and the willingness to sign a written informed consent document.

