15. Is pregnant or breastfeeding or expecting to conceive or father children within the projected duration of the trial, starting with the screening visit through 24 weeks after the last dose of trial treatment.
16. Has a history of Human Immunodeficiency Virus (HIV) (HIV 1/2 antibodies).
17. Has active Hepatitis B or Hepatitis C
18. Has a history of a solid organ transplant.

Inclusion of Women and Minorities

Women and members of minority groups and their subpopulations will be included in this study.

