6.4.4.1 CONTRACEPTION GUIDANCE FOR FEMALE PARTICIPANTS OF CHILD BEARING POTENTIAL

One of the highly effective methods of contraception listed below is required during study duration and until the end of relevant systemic exposure, defined as 24 weeks after the end of study treatment.*

Highly Effective Contraceptive Methods That Are User Dependent

Failure rate of <1% per year when used consistently and correctly.^a

- Combined (estrogen- and progestogen-containing) hormonal contraception associated with inhibition of ovulation^b
 - oral
 - intravaginal
 - transdermal
- Progestogen-only hormonal contraception associated with inhibition of ovulation
 - oral
 - injectable

Highly Effective Methods That Are User Independent

- Implantable progestogen-only hormonal contraception associated with inhibition of ovulation ^b
- Hormonal methods of contraception including oral contraceptive pills containing a combination of estrogen and progestrone, vaginal ring, injectables, implants and intrauterine hormone-releasing system (IUS)^c
- Intrauterine device (IUD)^c
- Bilateral tubal occlusion
- Vasectomized partner
A vasectomized partner is a highly effective contraception method provided that the partner is the sole male sexual partner of the WOCBP and the absence of sperm has been confirmed. If not, an additional highly effective method of contraception should be used.
- Sexual abstinence
Sexual abstinence is considered a highly effective method only if defined as refraining from heterosexual intercourse during the entire period of risk associated with the study drug. The reliability of sexual abstinence needs to be evaluated in relation to the duration of the study and the preferred and usual lifestyle of the participant.
- It is not necessary to use any other method of contraception when complete abstinence is elected.
- WOCBP participants who choose complete abstinence must continue to have pregnancy tests, as specified in Section 2.
- Acceptable alternate methods of highly effective contraception must be discussed in the event that the WOCBP participants chooses to forego complete abstinence

NOTES:

^a Typical use failure rates may differ from those when used consistently and correctly. Use should be consistent with local regulations regarding the use of contraceptive methods for participants participating in clinical studies.

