^b Hormonal contraception may be susceptible to interaction with the study drug, which may reduce the efficacy of the contraceptive method. Hormonal contraception is permissible only when there is sufficient evidence that the IMP and other study medications will not alter hormonal exposures such that contraception would be ineffective or result in increased exposures that could be potentially hazardous. In this case, alternative methods of contraception should be utilized.

^c Intrauterine devices and intrauterine hormone releasing systems are acceptable methods of contraception in the absence of definitive drug interaction studies when hormone exposures from intrauterine devices do not alter contraception effectiveness

Unacceptable Methods of Contraception*

- Male or female condom with or without spermicide. Male and female condoms cannot be used simultaneously
- Diaphragm with spermicide
- Cervical cap with spermicide
- Vaginal Sponge with spermicide
- Progestogen-only oral hormonal contraception, where inhibition of ovulation is not the primary mechanism of action
- Periodic abstinence (calendar, symptothermal, post-ovulation methods)
- Withdrawal (coitus interruptus)
- Spermicide only
- Lactation amenorrhea method (LAM)

* Local laws and regulations may require use of alternative and/or additional contraception methods.

6.4.4.2 CONTRACEPTION GUIDANCE FOR MALE PARTICIPANTS WITH PARTNER(S) OF CHILD BEARING POTENTIAL.

Male participants with female partners of childbearing potential are eligible to participate if they agree to the following during the treatment and until the end of relevant systemic exposure.

- Inform any and all partner(s) of their participation in a clinical drug study and the need to comply with contraception instructions as directed by the investigator.
- Male participants are required to use a condom for study duration and until end of relevant systemic exposure defined as 33 weeks after the end of study treatment.
- Female partners of males participating in the study to consider use of effective methods of contraception until the end of relevant systemic exposure, defined as 7 months after the end of treatment in the male participant.
- Male participants with a pregnant or breastfeeding partner must agree to remain abstinent from penile vaginal intercourse or use a male condom during each episode of penile penetration during the treatment and until 33 weeks after the end of study treatment.

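### Section 6.4.4.2 ends male contraception at both 33 weeks and 7 months, and the 5.1 entry criteria do not carry the methods that 6.4.4 requires

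*Combined protocol and SAP*

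**What the plan says.** **Women.** Section 5.1, inclusion criterion 11: "Female subjects of childbearing potential should be willing to use 1 method of birth control or abstain from heterosexual activity", and this "for the course of the study through 24 weeks after the last dose of study medication". No type of method is named and there is no reference to 6.4.4. Section 6.4.4.1: "One of the highly effective methods of contraception listed below is required during study duration and until the end of relevant systemic exposure", which it also sets at 24 weeks. The same section then lists unacceptable methods. One entry is "Diaphragm with spermicide"; others are condoms, cervical cap, sponge, periodic abstinence, withdrawal and spermicide alone.

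**Men.** Section 5.1, inclusion criterion 12, asks for a method that is adequate, without naming a type, "starting with the first dose of study therapy through 7 months after the last dose of study therapy". Section 6.4.4.2 requires a condom for the study and until the "end of relevant systemic exposure defined as 33 weeks after the end of study treatment". A later bullet applies the same 33 weeks to men with a pregnant or breastfeeding partner. Between those two, the bullet on female partners' contraception uses the same exposure end point but sets it at 7 months. The sperm-donation bullet also says 7 months.

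**Both sexes.** Section 5.2, exclusion criterion 15, excludes anyone who is pregnant, breastfeeding, or expecting to conceive or to father a child, "starting with the screening visit through 24 weeks after the last dose of trial treatment".

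**The concern.** These are operative participant-safety rules, and two places that should agree do not.

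A site that applies section 5 literally can enrol a woman whose only method is one that 6.4.4.1 rejects. It can also accept a man's undertaking to stop at 7 months, although 6.4.4.2 asks for condom use beyond that. Registration under section 6.2 turns on confirming eligibility, and nothing in section 5 sends the reader to 6.4.4. Section 7.6 applies the inclusion and exclusion criteria again before a second treatment (exclusion criterion 2 excepted), so the wording is used more than once.

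The conflict inside 6.4.4.2 is harder to excuse, because giving one section priority over another cannot settle it.

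What is at stake is possible fetal exposure to study antibodies. Under section 6.5 a pregnancy on treatment means removal from the study, and under section 9.1 it is handled as a serious adverse event. No endpoint, sample size or analysis is involved.

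**Working it through.** The plan computes nothing here, so the check is to set the texts side by side and put the durations in one unit.

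**Conversion to days**
- 24 weeks: 24 × 7 = 168 days.
- 33 weeks: 33 × 7 = 231 days.
- 7 calendar months: 212 to 215 days, depending on the starting month (212 / 7 = 30.3 weeks; 215 / 7 = 30.7 weeks).

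**Men**

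| Place | Subject of the rule | Limit | Days | Counted from |
|---|---|---|---|---|
| 5.1, criterion 12 | contraception, adequate method | 7 months | 212–215 | last dose |
| 6.4.4.2 | condom | 33 weeks | 231 | end of treatment |
| 6.4.4.2 | partners' contraception | 7 months | 212–215 | end of treatment |
| 6.4.4.2 | pregnant or breastfeeding partner | 33 weeks | 231 | end of treatment |
| 6.4.4.2 | sperm donation | 7 months | 212–215 | end of treatment |

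The gap between 33 weeks and 7 months is 231 − 215 = 16 days to 231 − 212 = 19 days. It cannot be a rounding of one unit to the other, since 7 months is closer to 30 or 31 weeks than to 33.

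The starting point adds an uncertainty between sections. The documents do not say whether the last dose and the end of study treatment are the same day. If they are, the gap between criterion 12 and the condom rule is 16 to 19 days. Suppose instead that a reader took the end of treatment as the end of the 28-day cycle begun by the last dose. This is an assumption and is not stated in the plan. It would add up to 28 days, so the gap could range from 16 to 19 + 28 = 47 days. The gap inside 6.4.4.2 stays at 16 to 19 days either way, because all its bullets count from the end of treatment.

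**Women**

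| Place | Method | Limit | Counted from |
|---|---|---|---|
| 5.1, criterion 11 | one method, type not named, or abstinence | 24 weeks | last dose |
| 6.4.4.1 | one from the highly effective list; others named as unacceptable | 24 weeks | end of treatment |

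The duration agrees at 168 days; only the starting-point wording differs. The methods do not agree. Take a woman whose single method is the diaphragm with spermicide: she has one method, so criterion 11 is met, and that method is on the unacceptable list, so 6.4.4.1 is not.

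**Exclusion criterion 15.** Its 24 weeks (168 days) is one number for both sexes. It equals the women's limit and falls 212 − 168 = 44 to 215 − 168 = 47 days short of the 7 months that criterion 12 sets for men. It concerns expecting to conceive or father a child, so it is a related limit and not a contraception duration.

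**The case against.** **The female criterion is under-specified, not contradictory.** Criterion 11 asks for one method; it does not say that any method will do and does not endorse a diaphragm. Section 6.4.4.1 can be read as supplying the detail, the durations match, and a woman can satisfy both texts. Much of this stands: a reader might infer that 5.1 expressly permits the rejected methods, and it does not. What remains is that the entry criterion can be met by a method rejected later, with no cross-reference to prevent it.

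**The male rules can be met together.** A man who uses a condom for 33 weeks satisfies every bullet, and the partner bullet only asks partners to consider contraception. True, but the protocol defines one end point twice, and a reader of criterion 12 alone would stop at 7 months.

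**Exclusion criterion 15 is not a third male limit.** A reader might infer three competing male durations with a spread of 33 − 24 = 9 weeks. The documents do not support that. The clause covers both sexes, concerns the intention to conceive or father, and applies together with criterion 12, so 7 months already binds a man at entry.

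**Exposure and testing.** A reader might infer exposure to three checkpoint antibodies. Each regimen contains two; all three are reached only in sequence, by a patient who qualifies for the other combination under 7.6. Nor is testing absent: it is required at screening, within a day before the first dose, and again with the 7.1 procedures before a second treatment. During treatment, however, the calendar footnotes provide for repeat tests only if pregnancy is suspected. The continued tests that 6.4.4.1 requires of abstinent women are referred to Section 2, which is the Background and contains no schedule.

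**How sites apply the criteria is not visible.** The eligibility checklist is not among the documents and the consent pages were removed, so it cannot be said that section 5 alone is applied in practice or that patients are counselled against 6.4.4.

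**Conclusion.** The contraception rules are internally inconsistent. The firmest part is within 6.4.4.2, where one exposure end point is both 33 weeks and 7 months, 16 to 19 days apart, with criterion 12 and the sperm-donation rule on the shorter side. Criterion 12 and 6.4.4.2 also differ on method and on starting point. For women the 24-week duration agrees, but criterion 11 can be met with a method that 6.4.4.1 rejects. Exclusion criterion 15 is a related limit to be checked by sex; it does not support a 9-week spread.

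The conclusion rests on the wording alone. The size in days assumes calendar months. The number of patients affected cannot be derived from the documents, but is likely to be small in a trial of 40. The point is worth correcting for participant and fetal safety and has no bearing on the analysis. No view is taken on which method or duration is right.

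**What to change.** The sponsor should reconcile inclusion criteria 11 and 12 (5.1), exclusion criterion 15 (5.2), 6.4.4.1 and every bullet of 6.4.4.2, so that:

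- the entry criteria and 6.4.4 state the same acceptable methods for each sex;
- each sex has one post-treatment limit, in one unit and from one defined starting point;
- 5.1 carries a cross-reference to 6.4.4;
- consent and eligibility-checklist text match.

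Exclusion criterion 15 needs care. It is a single clause for both sexes and its 24 weeks now agrees with the women's limit. If the male value is to be reflected there, the clause should be split by sex so that no new inconsistency arises for women. The sponsor chooses the methods and the values.

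The cost is wording in 5.1, 5.2 and 6.4.4 and the matching consent and checklist text. Sample size, endpoints, monitoring rules and analysis are unchanged.

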5.2 EXCLUSION CRITERIA

1. SCC of salivary gland origin or cutaneous SCC of the head and neck. HNSCC of unknown origin ARE eligible.
2. Patients who received Ipilimumab or Relatlimab in the recurrent/metastatic setting will be excluded.
3. Is currently participating in or has participated in a study of an investigational agent or used an investigational device within 2 weeks of the first dose of treatment.
4. Has a diagnosis of immunodeficiency or is receiving systemic steroid therapy (equivalent of ≥ 10 mg of prednisone) or any other form of immunosuppressive therapy within 7 days prior to the first dose of trial treatment.
5. Has had a prior monoclonal antibody, chemotherapy, or targeted small molecule therapy within 2 weeks prior to study Day 1 or who has not recovered (i.e., \leq Grade 1 or at baseline) from adverse events due to agents administered more than 4 weeks earlier (alopecia is an exception). Note: Subjects with \leq Grade 2 neuropathy, ototoxicity, hypothyroidism or hyperthyroidism, are an exception to this criterion and qualify for the study.
6. History of other malignancy within 3 years with the exception of prior HNSCC, adequately treated basal cell or squamous cell skin cancer, or carcinoma of the cervix.
7. Has an active autoimmune disease requiring systemic immunosuppressive treatment within the past 3 months. Subjects with vitiligo, Grave's disease, or psoriasis not requiring systemic therapy or resolved childhood asthma/atopy would be an exception to this rule. Subjects that require intermittent use of bronchodilators or local steroid injections would not be excluded from the study. Subjects with hypothyroidism stable on hormone replacement or Sjorgen's syndrome will not be excluded from the study.
8. Uncontrolled or significant cardiovascular disease including, but not limited to, any of the following:
 - a. Myocardial infarction (MI) or stroke/transient ischemic attack (TIA) within the 6 months prior to consent;
 - b. Uncontrolled angina within the 3 months prior to consent;
 - c. Any history of clinically significant arrhythmias (such as ventricular tachycardia, ventricular fibrillation, torsades de pointes, or poorly controlled atrial fibrillation);
 - d. QTc prolongation > 480 msec;
 - e. History of other clinically significant cardiovascular disease (i.e., cardiomyopathy, congestive heart failure with New York Heart Association [NYHA] functional classification III-IV, pericarditis, significant pericardial effusion, significant coronary stent occlusion, poorly controlled deep venous thrombosis, etc.);
 - f. Cardiovascular disease-related requirement for daily supplemental oxygen
 - g. History of two or more MIs OR two or more coronary revascularization procedures
 - h. Subjects with history of myocarditis, regardless of etiology.

9. A confirmed history of encephalitis, meningitis, or uncontrolled seizures in the year prior to informed consent
10. Subjects with history of life-threatening toxicity related to prior immune therapy (eg. anti-CTLA-4 or anti-PD-1/PD-L1 treatment or any other antibody or drug specifically targeting T-cell co-stimulation or immune checkpoint pathways) except those that are unlikely to re-occur with standard countermeasures (eg, hormone replacement after endocrinopathy).
11. Troponin T (TnT) or I (TnI) $> 2 \times$ institutional ULN. Subjects with TnT or TnI levels between > 1 to $2 \times$ ULN will be permitted if repeat levels within 24 hours are $\leq 1 \times$ ULN. If TnT or TnI levels are > 1 to $2 \times$ ULN within 24 hours, the subject may undergo a cardiac evaluation and be considered for treatment based on the discretion of the PI. When repeat levels within 24 hours are not available, a repeat test should be conducted as soon as possible. If TnT or TnI repeat levels beyond 24 hours are $< 2 \times$ ULN, the subject may undergo a cardiac evaluation and be considered for treatment, based on the discretion of the PI.
12. Has a history of non-infectious pneumonitis that required steroids, evidence of interstitial lung disease, or currently active non-infectious pneumonitis.
13. Has a history or current evidence of any condition, therapy, or laboratory abnormality that might confound the results of the trial, interfere with the subject's participation for the full duration of the trial, or is not in the best interest of the subject to participate, in the opinion of the treating investigator.
14. Has known psychiatric or substance abuse disorders that would interfere with cooperation with the requirements of the trial.
15. Is pregnant or breastfeeding or expecting to conceive or father children within the projected duration of the trial, starting with the screening visit through 24 weeks after the last dose of trial treatment.
16. Has a history of Human Immunodeficiency Virus (HIV) (HIV 1/2 antibodies).
17. Has active Hepatitis B or Hepatitis C
18. Has a history of a solid organ transplant.

Inclusion of Women and Minorities

Women and members of minority groups and their subpopulations will be included in this study.

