12.3 ADVERSE EVENT TREATMENT DISCONTINUATION CRITERIA

1. Any Grade ≥ 2 drug-related uveitis, eye pain or blurred vision that does not respond to topical therapy and does not improve to Grade 1 severity within the re-treatment period OR requires systemic treatment
2. Any Grade ≥ 3 non-skin, drug-related AE lasting > 7 days, or recurs with the following exceptions for laboratory abnormalities, diarrhea, colitis, neurologic toxicity, drug-related uveitis, pneumonitis, bronchospasm, hypersensitivity reactions, infusion reactions, and endocrinopathies:
 - a. Grade ≥ 3 drug-related myocarditis, diarrhea, colitis, neurologic toxicity, uveitis, pneumonitis, bronchospasm, hypersensitivity reaction, or infusion reaction of any duration requires discontinuation:-- Grade ≥ 3 drug-related endocrinopathies, adequately controlled with only physiologic hormone replacement do not require discontinuation. Adrenal insufficiency requires discontinuation regardless of control with hormone replacement.
 - b. Grade > 3 drug-related laboratory abnormalities do not require treatment discontinuation except:
 - i. Grade > 3 drug-related thrombocytopenia > 7 days or associated with bleeding requires discontinuation
 - c. Any drug-related liver function test (LFT) abnormality that meets the following criteria require discontinuation:
 - i. Grade > 3 drug-related AST, ALT or Total Bilirubin requires discontinuation*
 - ii. Concurrent AST or ALT $> 3 \times$ ULN and total bilirubin $> 2 \times$ ULN
- * In most cases of Grade 3 AST or ALT elevation, study treatment will be permanently discontinued. If the investigator determines a possible favorable benefit/risk ratio that warrants continuation of study treatment, a discussion between the investigator and the Sponsor
3. Any Grade 4 drug-related adverse event or laboratory abnormality (including but not limited to creatinine, AST, ALT, or Total Bilirubin), except for the following events which do not require discontinuation:
 - Grade 4 neutropenia ≤ 7 days
 - Grade 4 lymphopenia or leukopenia or asymptomatic amylase or lipase
 - Isolated Grade 4 electrolyte imbalances/abnormalities that are not associated with clinical sequelae and are corrected with supplementation/appropriate management within 72 hours of their onset

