12.5 CRITERIA TO RESUME TREATMENT

Subjects may resume treatment with combination therapy when the drug-related AE(s) resolve(s) to Grade \leq 1 or baseline and if applicable the patient is no longer on systemic steroids, with the following exceptions:

- Subjects may resume treatment in the presence of Grade 2 fatigue.
- Subjects who have not experienced a Grade 3 drug-related skin AE may resume treatment in the presence of Grade 2 skin toxicity.
- For participants with Grade 2 AST, ALT and/or Total Bilirubin Abnormalities, dosing may resume when laboratory values return to baseline and management with corticosteroids, if needed, is complete.
- Drug-related pulmonary toxicity, diarrhea, or colitis must have resolved to baseline before treatment is resumed. Subjects with persistent Grade 1 pneumonitis after completion of a steroid taper over at least 1 month may be eligible for retreatment if discussed with and approved by the Sponsor.

Participants with drug-related endocrinopathies adequately controlled with only physiologic hormone replacement may resume treatment after consultation with the Sponsor.

Adrenal insufficiency requires discontinuation regardless of control with hormone replacement.

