15.3.2 MONITORING RULE FOR EXCESS TOXICITY

Pausing rule: Adverse events sufficient to warrant discontinuation of treatment (Section 12.3) will be monitored in a similar fashion. If, where π indicates the probability of the specified adverse events, at any of these analyses,

$$\Pr(\Pr[\pi|\text{Data and Prior}] > 0.20) > 0.75,$$

Accrual to the trial will be paused and the protocol potentially amended. This is summarized in Table 9.

# Patients	Pause if #Tox \geq
10	3
20	5
30	7

Table 9. Pausing Rule in terms of number of patients with adverse events sufficient to warrant discontinuation of their treatment

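### Exclusion 5 sets a 2-week washout but requires recovery only from agents given more than 4 weeks earlier, so unresolved toxicity from an agent given only 15 to 28 days before Day 1 falls through

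*Combined protocol and SAP*

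**What the plan says.** Section 5.2, exclusion 5, has two parts joined by an *or*. The first is a washout: "Has had a prior monoclonal antibody, chemotherapy, or targeted small molecule therapy within 2 weeks prior to study Day 1". The second is a recovery requirement, to Grade 1 or lower or to baseline, but it is limited to recovery "from adverse events due to agents administered more than 4 weeks earlier (alopecia is an exception"). A note then tolerates neuropathy, ototoxicity, hypothyroidism and hyperthyroidism up to Grade 2.

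Section 7.6 applies all entry criteria again, except exclusion 2, before a second on-study treatment, so the same wording is used twice.

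For patients already on study, section 12.5 sets the standard for giving the next dose: "Subjects may resume treatment with combination therapy when the drug-related AE(s) resolve(s) to Grade" 1 or lower, or baseline, with exceptions for Grade 2 fatigue and some Grade 2 skin toxicity. It is stricter for some events: "Drug-related pulmonary toxicity, diarrhea, or colitis must have resolved to baseline before treatment is resumed".

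Section 15.3.2 defines what feeds the safety pausing rule: "Adverse events sufficient to warrant discontinuation of treatment (Section 12.3) will be monitored in a similar fashion". Table 9 pauses accrual at 3 events in 10 patients, 5 in 20 or 7 in 30.

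**The concern.** A recovery rule normally begins where the washout ends. Here it begins two weeks further back, so recovery is required from older agents and not from the most recent permitted ones. Nothing in the protocol explains this. The list of tolerated Grade 2 toxicities suggests it was not intended, because the list has a purpose only if other Grade 2 toxicity is meant to exclude.

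The window matters in this population. Every patient must have progressed on an anti-PD-1 or anti-PD-L1 antibody (inclusion 2a). Section 2.3.7 gives single-agent nivolumab dosing as every 2 or every 4 weeks, and section 2.3.2 gives a half-life of 26.7 days. A last dose 15 to 28 days before Day 1 is therefore plausible.

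Two things are at stake. The first is patient safety and consistent eligibility decisions: two coordinators could decide the same patient differently. The second is smaller. Carried-over toxicity that later meets section 12.3 and is attributed to study drug would count toward Table 9 as though the combination had caused it.

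**Working it through.** **Step 1. Set the two parts of exclusion 5 on one time line.** Two weeks is 2 × 7 = 14 days; four weeks is 4 × 7 = 28 days.

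| Days before Day 1 on which the agent was given | Washout excludes? | Recovery to Grade 1 or baseline required? |
|---|---|---|
| 0–14 | Yes | Not needed |
| 15–28 | No | No |
| 29 or more | No | Yes |

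The uncovered window is 28 − 14 = 14 days. For an agent given only in that window the gap is unambiguous. For a repeat-dosed agent it depends on whether *administered more than 4 weeks earlier* refers to the first dose (covered) or the last dose (not covered), which the text does not say.

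**Step 2. Check whether another criterion closes the window.**

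- ECOG 0–1 and inclusion 10 cover performance status and marrow, liver and renal laboratory values.
- Inclusion 9 covers ejection fraction.
- Exclusion 4 covers steroids of 10 mg prednisone equivalent or more, or other immunosuppression, within 7 days.
- Exclusion 7 covers active autoimmune disease that needed systemic immunosuppression in the past 3 months.
- Exclusions 8h, 9, 10, 11 and 12 cover myocarditis, encephalitis or meningitis, life-threatening immune toxicity, troponin and pneumonitis.
- Exclusion 13 covers any condition for which entry "is not in the best interest of the subject to participate, in the opinion of the treating investigator". It has no grade threshold.

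Grade 2–3 diarrhoea or arthritis, or Grade 3 rash, in a patient not on steroids or immunosuppression meets no fixed rule. Only exclusion 13 remains.

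**Step 3. Compare with the on-study standard.** Section 12.2 requires study drugs to be held for drug-related diarrhoea or colitis of Grade 2 or higher and skin events of Grade 3 or higher. Section 12.5 then requires return to baseline for diarrhoea or colitis, and Grade 1 or baseline in general. Exclusion 5 would admit a patient to a first dose at the grades that trigger a hold.

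**Step 4. Illustrate the effect on the toxicity pause.** The protocol gives no figure to reproduce here. Inputs from the protocol: Table 9 limits of 3/10, 5/20 and 7/30. Inputs assumed: a true event rate *p* of 10% or 15%, and exactly one carry-over patient among the first ten, with event risk *q* of 30%, 50% or 100%; everyone else has risk *p*.

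At the first look, with X the number of events in the other nine patients, X ~ Bin(9, *p*):

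P(pause at 10) = (1 − *q*) · P(X ≥ 3) + *q* · P(X ≥ 2)

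For *p* = 0.10, P(X ≥ 3) = 0.053 and P(X ≥ 2) = 0.225. With *q* = 0.5 this is 0.5 × 0.053 + 0.5 × 0.225 = 0.139. Without a carry-over patient it is P(Bin(10, 0.10) ≥ 3) = 0.070. Paths that have not paused are carried forward through the looks at 20 and 30, and the pause probabilities are added over the three looks:

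| True rate *p* | No carry-over | *q* = 30% | *q* = 50% | *q* = 100% |
|---|---|---|---|---|
| 10% | 0.096 | 0.134 | 0.172 | 0.268 |
| 15% | 0.285 | 0.325 | 0.379 | 0.513 |

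The *q* = 100% column is an upper bound, not an estimate.

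**The case against.** The strongest reply is that the certain gap is narrow. The recovery clause speaks of agents, not last doses. A checkpoint inhibitor started more than 4 weeks before Day 1 was administered more than 4 weeks earlier, even if a later dose fell on days 15 to 28. On that reading only an agent first given in the window escapes. Such a patient would also need a biopsy after that agent (inclusion 6) and would wait about 5 business days for the assay report (section 14.1.1). This reading is open, but the text does not settle it, and the first-dose-in-window case remains either way.

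Second, exclusion 13 is a binding criterion, many immune toxicities would be on steroids and so caught by exclusion 4, and section 12.2 lets the investigator delay a dose for any adverse event. This reduces the practical risk. It does not supply the fixed Grade 1 or baseline rule that exclusion 5 applies to older agents.

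Third, section 12.5 governs events related to the study drugs, so the comparison is not like for like. That is right: it is a mismatch of standards, not a contradiction.

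Fourth, the pause probabilities rest on assumed inputs. To count through item 2 of section 12.3, an event must be drug-related and a Grade 3 or higher "non-skin, drug-related AE lasting > 7 days, or recurs with the following exceptions". Grade 3 rash would not count there, and a trigger only pauses accrual. All of that stands, so the figures are illustrative and the case does not depend on them.

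**Conclusion.** The concern holds. On its literal wording, exclusion 5 requires no recovery from toxicity due to an agent given only 15 to 28 days before Day 1, and its meaning for repeat-dosed agents is unclear. No other criterion sets a general grade limit for that window.

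The main consequence is for safety and consistent eligibility decisions, both at entry and before second treatment. The effect on the toxicity pausing rule is secondary. Under the assumption of one carry-over patient in the first ten, it adds between 0.134 − 0.096 = 0.038 and 0.268 − 0.096 = 0.172 to the chance of a pause at a true rate of 10%, and between 0.325 − 0.285 = 0.040 and 0.513 − 0.285 = 0.228 at 15%. The documents give neither the number of such patients nor their event risk. Sample size, the primary analysis and the stated operating characteristics are unaffected. The change should be made, but the trial's conclusions do not hinge on it.

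**What to change.** In exclusion 5, make the recovery clause apply to adverse events due to *any previously administered agent*. Changing 4 weeks to 2 weeks in that clause would also close the window, but naming any previously administered agent is better because it removes the question of which dose counts. Keep the Grade 1 or baseline limit, the alopecia exception and the tolerated Grade 2 toxicities. Section 7.6 picks up the change without further editing.

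The cost is one phrase in an amendment. A few patients may have to wait for recovery or may not be enrolled.
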